8.1.2.2 Ordinal Scale

The ordinal scale is the primary measure of clinical outcome.

The scale used in this study is as follows (from worst to best):

- Death;
- Hospitalized, on invasive mechanical ventilation or ECMO;
- Hospitalized, on non-invasive ventilation or high flow oxygen devices;
- Hospitalized, requiring supplemental oxygen;
- Hospitalized, not requiring supplemental oxygen – requiring ongoing medical care (COVID-19 related or otherwise);
- Hospitalized, not requiring supplemental oxygen – no longer requires ongoing medical care;
 - This would include those kept in hospital for quarantine/infection control, awaiting bed in rehabilitation facility or homecare, etc.
- Not hospitalized, limitation on activities and/or requiring home oxygen;
- Not hospitalized, no limitations on activities

To determine a subject's clinical status using the ordinal scale: On Day 1, report their clinical status at randomization. As there should be <24 hours between randomization and infusion, the ordinal scale at done at randomization suffices as the Day 1 ordinal scale. After Day 1, collect the ordinal scale daily while hospitalized from Day 2 through Day 29 by providing the worst clinical assessment for the previous day (i.e., midnight to midnight; 00:00 – 23:59 (24-hr clock)). For those who are discharged prior to Day 15, collect ordinal scale on follow-up Days 15, 22 and 29 by providing the worst clinical assessment for the previous day (i.e., midnight to midnight; 00:00 – 23:59 (24-hr clock)). For example, on study Day 3 when completing the form, the worse

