4.3. Efficacy and Safety Variables

For each study day while the patient is hospitalized, the clinical status will be recorded on an 8-point ordinal scale as follows:

- Day 1 – The clinical assessment at the time of randomization.
- Day 2 + - The most severe assessment occurring from midnight to midnight (00:00 to 23:59) of the prior day (e.g., the value recorded on Day 3 will be the most severe outcome that occurred on Day 2).

where the clinical status scale is defined as follows:

- 8. Death;

7. Hospitalized, on invasive mechanical ventilation or ECMO;
6. Hospitalized, on non-invasive ventilation or high flow oxygen devices;
5. Hospitalized, requiring supplemental oxygen;
4. Hospitalized, not requiring supplemental oxygen- requiring ongoing medical care (COVID-19 related or otherwise);
3. Hospitalized, not requiring supplemental oxygen - no longer requires ongoing medical care;
2. Not hospitalized, limitation on activities;
1. Not hospitalized, no limitations on activities

A modified version of the ordinal scale will be used in sensitivity analyses of the primary and secondary outcomes. The modified scale will be as follows:

8. Death;
7. Hospitalized, on invasive mechanical ventilation or ECMO;
6. Hospitalized, on non-invasive ventilation or high flow oxygen devices;
5. Hospitalized, requiring supplemental oxygen;
4. Hospitalized, not requiring supplemental oxygen- requiring ongoing medical care (COVID-19 related or otherwise);
3. Not hospitalized, limitation on activities;
2. Hospitalized, not requiring supplemental oxygen - no longer requires ongoing medical care; or Not hospitalized, no limitations on activities.

That is, category 1 and 3 of the original scale will be combined into the lowest category.

NEWS has demonstrated an ability to discriminate subjects at risk of poor outcomes. This score is based on 7 clinical parameters (see Section 8.1.2.3 in Appendix B of the study protocol). This should be evaluated at the first assessment of a given study day and prior to administration of study product. The 7 parameters can be obtained from the hospital chart using the last measurement prior to the time of assessment and a numeric score given for each parameter (e.g., a RR of 9 is one point, oxygen saturation of 92 is two points). This is recorded for the day obtained. i.e., on Day N, the Day N score is obtained and recorded as the Day N score.

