6.5. Missing Data

All attempts will be made to collect all data per protocol. Any data point that appears to be erroneous or inexplicable based on clinical judgment will be investigated as a possible outlier. If data points are identified as outliers, sensitivity analyses may be performed to examine the impact of including or excluding the outliers. Any substantive differences in these analyses will be reported.

For time to event outcomes, subjects who are lost to follow-up or terminate the study prior to Day 29 and prior to observing/experiencing the event will be censored at the time of their last observed assessment. Subjects who die prior to observing/experiencing the event will be censored at Day 29.

For the analysis of the key secondary outcome, subjects who are discharged but are subsequently re-admitted prior to Day 15 without a reported clinical score, their clinical score will be imputed at 7, which is the highest value for a hospitalized subject.

For the analyses of the secondary outcomes that involve clinical score (i.e. the key secondary outcome and time to improvement), if a subject is discharged from the hospital without a previously or concurrently reported clinical score of 1 or 2, then their clinical score at the time of discharge will be imputed as 2, which is the highest value for a non-hospitalized subject. If a subject terminates early from the study while they are hospitalized or completes the study while still hospitalized, the last observed clinical score assessment will be used as their final assessment.

For the modified version of the ordinal score described in Section 4.3, if a subject is discharged from the hospital without a previously or concurrently reported clinical score of 2 or 3, then their clinical score at the time of discharge will be imputed as 3, which is the highest value for a non-hospitalized subject.

For the analyses of the secondary outcomes described in Section 3.3, the following imputation rules will be used for subjects who are lost to follow-up, terminate early from the study, or do not have further outcome data available after discharge for any reason:

- Days of Non-invasive ventilation/high-flow oxygen:

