The number and proportion of subjects along with 95% confidence intervals by category of clinical status will be presented by treatment arm at Study Visit (not necessarily actual) Days 1, 3, 5, 8, 11, 15 and 29 (Table 33). Change from baseline will also be summarized at Days 3, 5, 7, 11, 15, 22, and 29 (Table 35). A figure will present stacked bar charts by day with side by side bars for each treatment arm (Figure 25). Histograms will be generated to display the ordinal scale value distributions over time in each treatment group (Figure 26).

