If necessary, a row for “No clinical status score reported – Completed study without reporting score” will be added as the last row for each day.

Table with similar format:

Table 34: Clinical Status Scores by Treatment Group and Study Visit – As Treated Population

Table 35: Summary of Clinical Status Score by Treatment Group and Study Visit – ITT Population

Study Visit	Statistic	Baricitinib + RDV (N=X)	Placebo + RDV (N=X)	All Subjects (N=C)
Baseline	Number of reported clinical scores	x	x	x
	Mean (SD)	x.x (x.x)	x.x (x.x)	x.x (x.x)
	Median	x.x	x.x	x.x
	Range (Min, Max)	x, x	x, x	x, x
Day 3	Number of reported clinical scores	x	x	x
	Mean (SD)	x.x (x.x)	x.x (x.x)	x.x (x.x)
	Median	x.x	x.x	x.x
	Range (Min, Max)	x, x	x, x	x, x
	Change from Baseline Mean (SD)	x.x (x.x)	x.x (x.x)	x.x (x.x)
Continue for Days 5, 8, 11, 15, 22, 29				
N = Number of subjects in the ITT Population. SD = Standard deviation. Missing values were imputed using Last Observation Carried Forward. Clinical scores of 8 were carried forward from the date of death for subjects who died.				

Table with similar format:

Table 36: Summary of Clinical Status Score by Treatment Group and Study Visit – As Treated Population

Table 37: Time to Discharge or to a NEWS of ≤ 2 by Treatment Group

Analysis Population	Treatment Group	n ^a	Median Time		HR		P-value
			Estimate	95% CI	Estimate	95% CI	
ITT Population	Baricitinib + RDV (N=X)	x	x.x	x.x, x.x	x.xx	x.xx, x.xx	x.xxx
	Placebo + RDV (N=X)	x	x.x	x.x, x.x			
As Treated Population	Baricitinib + RDV (N=X)	x	x.x	x.x, x.x	x.xx	x.xx, x.xx	x.xxx
	Placebo + RDV (N=X)	x	x.x	x.x, x.x			

N= Number of subjects in the specified treatment group and analysis population.
n = Number of subjects who discharged or had a NEWS of ≤ 2 prior to Day 29.
HR is the ratio of the hazard of discharge or NEWS of ≤ 2 in each treatment group estimated from the Cox model. The ratio is Baricitinib + RDV to Placebo + RDV. P-value calculated using the Log-rank test

Tables with similar format:

Table 38: Time to Discharge or to a NEWS of ≤ 2 by Treatment Group within Subgroups – ITT Population

Table 39: Time to Discharge or to a NEWS of ≤ 2 by Treatment Group within Subgroups – As Treated Population

Programming notes for Tables 38 – 39: “Subgroup Category” and “Subgroup” columns will replace the “Analysis Population” column to the left of “Treatment Group”. Rows will be repeated for each subgroup. P-values will not be displayed in these tables.

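### Tables 35 and 36 carry the last inpatient score past discharge, which blunts mean change from Day 1 at Days 3 to 11

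*SAP*

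**What the plan says.** SAP Section 3.1 lists mean change in the 8-point score from Day 1 among the secondary objectives. Section 8.2.1 assigns it to a table: "Change from baseline will also be summarized at Days 3, 5, 7, 11, 15, 22, and 29 (Table 35". (The Table 35 shell uses Day 8 where this sentence has Day 7.)

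The Table 35 footnote gives the missing-data rule, and Table 36 has the same format: "Missing values were imputed using Last Observation Carried Forward". One special case follows: "Clinical scores of 8 were carried forward from the date of death for subjects who died". Discharge is not mentioned.

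Three other places determine what that rule does:

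- **When scores exist.** Protocol Appendix B, Section 8.1.2.2, has the scale completed daily in hospital. After that: "For those who are discharged prior to Day 15, collect ordinal scale on follow-up Days 15, 22 and 29".
- **What a score describes.** SAP Section 4.3, for Day 2 onward: "The most severe assessment occurring from midnight to midnight (00:00 to 23:59) of the prior day".
- **The discharge rule.** SAP Section 6.5 covers anyone sent home with neither of the two outpatient scores on record. For such a person the rule reads: "then their clinical score at the time of discharge will be imputed as 2". It applies to the "secondary outcomes that involve clinical score (i.e. the key secondary outcome and time to improvement").

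**The concern.** A subject who goes home on Day 6 has no scheduled score at Days 8 and 11. The last form normally describes an inpatient day, so its score is 3 or higher. Carry-forward places that score in the Day 8 and Day 11 means, although the discharge date shows that the subject was in category 1 or 2. This is a known misclassification, not a guess about unknown data.

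There are two consequences. Improvement is understated in both arms. And if one arm discharges faster, more of its subjects carry a score that is too severe, so the arm means are pulled together. A harmful effect on discharge would be diluted in the same way. The SAP would also be inconsistent with itself: the same subject could count as 2 for time to improvement and as 4 or 5 in Table 35.

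**Working it through.** **Design figure.** The documents give no figure for Tables 35 and 36. The illustration borrows the design rate ratio of 1.25 (SAP Section 5), so that calculation was checked first: 4 × (1.96 + 1.0364)² / (ln 1.25)² = 721.3, or 722 recoveries rounded up, against 723 stated; 723 / 0.70 = 1032.9, against 1032 stated. Both agree to rounding.

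**Which visits are affected.** Days 3, 5, 8 and 11, and only after the subject's own discharge. Days 15, 22 and 29 have scheduled post-discharge scores and are affected only if the visit is missed. Table 33 anticipates the gap: it has a row at each visit for discharged subjects with no reported score.

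**Assumptions (not document figures).** Exponential discharge times; discharge rate ratio 1.25 (the SAP's ratio is for recovery); control median m = 6, 8 or 11 days; every subject at baseline 5; score 2 at home; the same scores in both arms for those still in hospital.

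**Formulas.**
- Share discharged by Day d: P = 1 − 0.5^(r(d − 1)/m), with r = 1 for control and 1.25 for baricitinib.
- Full difference due to discharge: −(5 − 2)(Pt − Pc).
- Difference under carry-forward of score c: −(5 − c)(Pt − Pc).
- Fraction kept: (5 − c)/3.

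**Day 8.**

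| Control median | Discharged, control | Discharged, baricitinib | Full difference | Carried 5 | Carried 4 | Carried 3 |
|---|---|---|---|---|---|---|
| 6 days | 0.555 | 0.636 | −0.245 | 0 | −0.082 | −0.163 |
| 8 days | 0.455 | 0.531 | −0.230 | 0 | −0.077 | −0.153 |
| 11 days | 0.357 | 0.424 | −0.202 | 0 | −0.067 | −0.134 |

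**Other visits.** The full difference is −0.08 to −0.13 at Day 3, −0.14 to −0.21 at Day 5 and −0.23 to −0.25 at Day 11. The fractions kept are the same at every visit: 0%, 33% and 67%.

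**Some subjects report a 2 at discharge.** With share q, the fraction kept is [(1 − q)(5 − c) + 3q]/3. For carried scores 5, 4 and 3, q = 25% gives 25%, 50% and 75%; q = 50% gives 50%, 67% and 83%.

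**No discharge in the first 3 days.** Anticipated discharge within 72 hours is an exclusion criterion. Replacing d − 1 by d − 4 (zero at Day 3) gives a full difference of 0 at Day 3, −0.04 to −0.08 at Day 5, −0.14 to −0.21 at Day 8 and −0.20 to −0.25 at Day 11, with the same fractions kept.

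**Within one arm.** At Day 8, 35.7% to 55.5% of control subjects are discharged. Carrying 4 instead of 2 raises the control mean by 2 × 0.357 = 0.71 to 2 × 0.555 = 1.11 points. This happens with or without a treatment effect.

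**Second set of assumptions.** With a mean score of 5.0 to 6.0 for subjects not discharged and a home score of 1.5, carry-forward keeps 57–67%, 29–44% or 0–22% of the true difference for carried scores of 3, 4 or 5. Assigning 2 at discharge keeps 86–89%. A simulation with mixed baseline scores 4 to 7 kept 26–30% under carry-forward and showed no spurious difference when the arms were equal.

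**The case against.** The best counter-argument is that Section 6.5 already covers this. Its rule opens with secondary outcomes that involve the clinical score, and mean change is one. If 2 is assigned at discharge first, carry-forward then carries 2 and the problem disappears. But the parenthesis lists two outcomes and mean change is not among them, Section 3.3.3 says by-visit analyses use the scores collected at those visits, and the footnote names death alone. At best, two programmers could follow the SAP and produce different tables.

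Other points stand as limits on the finding:

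- Nothing in the documents says how often a 1 or 2 is recorded at discharge. Those subjects are carried forward correctly.
- Mean change is in the objectives but not in the Section 3.2 endpoint list, and the SAP change log calls the outputs added in version 3.0 supplemental and exploratory.
- Table 35 shows no between-arm difference, interval or p-value, and it prints the number of reported scores at each visit.
- The size rests on assumed inputs. With a carried score of 4, a baseline of 6 keeps (6 − 4)/(6 − 2) = 50% and a baseline of 7 keeps (7 − 4)/(7 − 2) = 60%, not 33%. Total loss needs a last inpatient score equal to baseline.

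These limits bound the effect; they do not make an inpatient score right for someone at home.

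**Conclusion.** The concern holds. Read literally, the footnote gives subjects known to be at home an inpatient score at Days 3 to 11, so the arm means are too severe and, if discharge speed differs, too close together. On the stated assumptions a Day 8 difference of 0.20 to 0.25 points shrinks to 0, to 0.07–0.08, or to 0.13–0.16, for carried scores of 5, 4 or 3; less is lost if some subjects report a 2 at discharge. The direction is firm whenever the arms differ in discharge speed. The size is illustrative, because neither the discharge times nor the last inpatient scores are in the documents. No false benefit is created, and the primary, Day 15 and time-to-improvement analyses are not touched.

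**What to change.** Add mean change to the outcomes named in the Section 6.5 discharge rule, and state the order of operations in the Table 35 and 36 footnotes:

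1. At discharge, use the reported 1 or 2, or 2 if neither was reported, and hold it until the next recorded score or readmission.
2. After death, carry 8 forward.
3. Carry an inpatient score forward only across gaps while the subject is in hospital.

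Also state which score applies after a readmission with no recorded score; Section 6.5 uses 7 for the Day 15 analysis. While editing, align Day 7 in Section 8.2.1 with Day 8 in the table shell.

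The cost is one phrase in Section 6.5 and one footnote in two table shells. Discharge and readmission data are already collected.

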3. STUDY OBJECTIVES AND ENDPOINTS

3.1. Study Objectives

Primary Objective

To evaluate the clinical efficacy, as assessed by time to recovery, of different investigational therapeutics as compared to the control arm.

Secondary Objectives

The key secondary objective is to evaluate the clinical efficacy of different investigational therapeutics relative to the control arm in adults hospitalized with COVID-19 according to clinical status (8-point ordinal clinical scale) at Day 15.

The other secondary objectives are to:

1. Evaluate clinical efficacy of different investigational therapeutics as compared to the control arm as assessed by:
 - Clinical Severity
 - 8-Point Clinical Status Ordinal scale:
 - Time to an improvement of one category and two categories from Day 1 (baseline) on the clinical status 8-point ordinal scale.
 - Subject clinical status using 8-point ordinal scale at Days 3, 5, 8, 11, 15, 22, and 29.
 - Mean change in the clinical status 8-point ordinal scale from Day 1 to Days 3, 5, 8, 11, 15, and 29.
 - National Early Warning Score (NEWS):
 - Time to discharge or to a NEWS of ≤ 2 and maintained for 24 hours, whichever occurs first.
 - Change from Day 1 to Days 3, 5, 8, 11, 15, and 29 in NEWS.
 - Oxygenation:
 - Oxygenation use up to Day 29.
 - Incidence and duration of new oxygen use through Day 29.
 - Non-invasive ventilation/high flow oxygen:
 - Non-invasive ventilation/high flow oxygen use up to Day 29.
 - Incidence and duration of new non-invasive ventilation or high flow oxygen use through Day 29.
 - Invasive Mechanical Ventilation / extracorporeal membrane oxygenation (ECMO):
 - Ventilator/ECMO use up to Day 29.
 - Incidence and duration of new mechanical ventilation or ECMO use through Day 29.

- Hospitalization
 - Duration of hospitalization (in days) through Day 29.
 - Mortality
 - 14-day mortality.
 - 28-day mortality.
2. Evaluate the safety of the intervention through 28 days of follow-up as compared to the control arm as assessed by:
- Cumulative incidence of SAEs through Day 29
 - Cumulative incidence of Grade 3 and 4 clinical and/or laboratory AEs through Day 29.
 - Discontinuation or temporary suspension of study product administrations (for any reason).

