8.2.4. Incidence of New Oxygen use

The incidence and duration of new oxygen use will be analyzed by treatment arm. This will only include subjects in category 4 at randomization. New use will be identified by a post-enrollment score of at least 5; the number of subjects reporting new use and the incidence rate (and CI) will be reported.

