8.2.6. Incidence of New Non-Invasive Ventilation/High-Flow Oxygen

The incidence and duration of new Non-Invasive Ventilation/High-Flow Oxygen use will be analyzed by treatment arm. This will only include subjects in category 4 or 5 at randomization. New use will be identified by a post-enrollment score of 6. The number of subjects reporting new use and the incidence rate (and CI) will be reported.

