8.2.8. Incidence of New Invasive Mechanical Ventilation/ECMO

The incidence and duration of new Invasive Mechanical Ventilation/ECMO use will be analyzed by treatment arm. This will only include subjects in category 4, 5, or 6 at randomization. New use will be identified by a post-enrollment score of 7. The number of subjects reporting new use and the incidence rate (and CI) will be reported.

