Table 40: Summary of NEWS by Treatment Group and Study Visit – ITT Population

Study Visit	Statistic	Baricitinib + RDV (N=X)	Placebo + RDV (N=X)	All Subjects (N = X)
Baseline	n	x	x	x
	Mean (SD)	x.x (x.x)	x.x (x.x)	x.x (x.x)
	Median	x.x	x.x	x.x
	Range (Min, Max)	x, x	x, x	x, x
Day 3	n	x	x	x
	Mean (SD)	x.x (x.x)	x.x (x.x)	x.x (x.x)
	Median	x.x	x.x	x.x
	Range (Min, Max)	x, x	x, x	x, x
	n ^a	x	x	x
	Change from Baseline Mean (SD)	x.x (x.x)	x.x (x.x)	x.x (x.x)
[Repeat for Study Visit Days 5, 8, 11, 15, 22, 29 and Change from Baseline at each]				
n = Number of subjects with an assessment at both baseline and the time point being summarized. n ^a = Number of subjects with an assessment at both baseline and the time point being summarized. SD = Standard deviation.				

Table with similar format:

Table 41: Summary of NEWS by Treatment Group and Study Visit – As Treated Population

Table 42: Oxygen Use by Treatment Group

Analysis Population	Oxygen Use	Statistic	Treatment Group	
			Baricitinib + RDV	Placebo + RDV
ITT Population	On Oxygen at Baseline (N = x)			
	Days on Oxygen (Including imputations for subjects who died)	N	x	x
		Q1	x.x	x.x
		Median	x.x	x.x
		Q3	x.x	x.x
	Days of Oxygen (Among subjects who did not die)	N	x	x
		Q1	x.x	x.x
		Median	x.x	x.x
		Q3	x.x	x.x
	Not on Oxygen at Baseline (N = x)			
	New Oxygen Use	N	x	x
		n	x	x
		Incidence Rate	x.x	x.x
		Incidence Rate CI	x.x, x.x	x.x, x.x
	Days on Oxygen (Including imputations for subjects who died)	N	x	x
		Q1	x.x	x.x
		Median	x.x	x.x
		Q3	x.x	x.x
	Days of Oxygen (Among subjects who did not die)	N	x	x
		Q1	x.x	x.x
Median		x.x	x.x	
Q3		x.x	x.x	
Continue for As Treated Population...				
N = Number of subjects in the specified analysis population and oxygen use category. Q1 and Q3 are the first and third quartiles, respectively.				

Programming Notes:

For the “Days on Oxygen” statistics within the “Not on Oxygen at Baseline” subgroup, only summarize days for subjects who reported new use.

Tables with similar format:

Table 43: Oxygen Use by Treatment Group within Subgroups

Table 44: Non-invasive Ventilation/High-Flow Oxygen Use by Treatment Group

Table 45: Non-invasive Ventilation/High-Flow Oxygen Use by Treatment Group within Subgroups

Table 46: Ventilation/ECMO Use by Treatment Group

Table 47: Ventilation/ECMO Use by Treatment Group within Subgroups

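### Duration of newly started oxygen or ventilatory support is summarized only among patients who started it, so these rows are not a randomized comparison and can mislead in either direction

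*SAP*

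**What the plan says.** The SAP lists "Incidence and duration of new oxygen use through Day 29" among its secondary objectives (Section 3.1), with parallel items for non-invasive/high-flow support and for invasive ventilation/ECMO. Section 8.2.4 states: "The incidence and duration of new oxygen use will be analyzed by treatment arm". Section 8.2.6 says "The incidence and duration of new Non-Invasive Ventilation/High-Flow Oxygen use will be analyzed by treatment arm", and Section 8.2.8 says "The incidence and duration of new Invasive Mechanical Ventilation/ECMO use will be analyzed by treatment arm". The at-risk sets are fixed by baseline category: 4 for oxygen, 4 or 5 for non-invasive/high-flow, and 4, 5 or 6 for invasive. New use is defined by a post-enrollment score.

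For patients not on oxygen at baseline, the Table 42 shell gives, by arm, the number at risk, the number with new use, and the incidence rate with a CI. Two duration blocks follow (N, Q1, median, Q3). One includes imputed values for deaths. The other is "Days of Oxygen (Among subjects who did not die"). The programming note limits the days statistics in this part of the table to new users: "only summarize days for subjects who reported new use". "Table 44: Non-invasive Ventilation/High-Flow Oxygen Use by Treatment Group", "Table 46: Ventilation/ECMO Use by Treatment Group" and the subgroup Tables 43, 45 and 47 are listed as having the same format.

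The other days-on-support summaries (Sections 8.2.3, 8.2.5, 8.2.7) cover only patients already on that support at randomization. Section 8.2 places all secondary efficacy analyses in the ITT population.

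**The concern.** Whether a patient starts support is an outcome of treatment. If one arm prevents some starts, its new users are a differently selected group, and a difference in their durations mixes selection with any real change in time on support. The ITT label on the block holds for the incidence row but not for the duration rows. Setting deaths to 28 days does not help, because the row is still limited to new users. The survivors-only row conditions on a second post-randomization event.

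For patients at risk of starting support, these rows are the only duration result in this SAP. A reader who takes the two medians as the answer to the duration objective could get the direction of effect wrong.

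**Working it through.** The documents state no incidence, duration or power for new support, so there is no planned figure to reproduce. All incidences and durations below are assumptions.

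**1. Two-class illustration.** Let p be the share of at-risk patients in each class and d the days on support; no deaths.
- Days among users = Σ(p × d) / Σp. Days per at-risk patient = Σ(p × d).
- Control, 10% mild at 5 days and 10% severe at 15 days: (0.10×5 + 0.10×15) / 0.20 = 2.0 / 0.20 = **10.0** among users; **2.0** per at-risk patient.
- Treatment, 4% mild and 8% severe: (0.04×5 + 0.08×15) / 0.12 = 1.4 / 0.12 = **11.7** among users; **1.4** per at-risk patient.
- Treatment lowers both kinds of progression and total days (1.4/2.0 = 0.70, 30% fewer), yet its new-user mean is 1.7 days longer.
- On the table's own statistic, control users split evenly between 5 and 15 days (midpoint 10), while 8/12 = 67% of treatment users are at 15, so the median is 15.

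**2. Other direction.** Swap the treatment shares to 8% mild and 4% severe: (0.08×5 + 0.04×15) / 0.12 = 1.0 / 0.12 = **8.3** among users against 10.0. No patient's spell on support is shorter; only the mix has changed. Also, reading step 1 with the arms exchanged, a treatment that causes extra starts looks better among users (10.0 against 11.7) while costing more days per at-risk patient (2.0 against 1.4).

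**3. Range.** Assume mild progressors average 4 days (SD 2), severe progressors 16 days (SD 6, capped at 28), and treatment prevents only mild progressions. Fifteen settings were run: control mild 10–35%, severe 10–30%, prevented share 25–75%.

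| Treatment minus control, no deaths | Range |
|---|---|
| Median days among new users | 0 to +7 |
| Mean days among new users | about +0.7 to +3.9 |
| Mean days over all at-risk patients | about −0.1 to −1.05 |

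One setting in full, with control 20% mild and 20% severe and half the mild progressions prevented: new-user median 8 (quartiles 4–15) on control and 12 (5–17) on treatment; all-at-risk mean 3.97 and 3.57; incidence 40% and 30%. Adding 5% deaths per arm at 28 days, counted as new users, leaves the direction unchanged.

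**4. Would zero-filled quartiles work?** At 20% and 12% incidence with no deaths, 80% and 88% of values are 0, so Q1, median and Q3 are 0 in both arms. In general the median is 0 when new users plus deaths without use are below 50% of those at risk, and all three quartiles are 0 when they are below 25%. An all-at-risk row therefore needs a mean or support-free days.

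**The case against.** The best case for the plan is that it does not treat these rows as a comparison. The shell shows quartiles by arm with no difference, hazard ratio or p-value. Protocol Appendix B Section 9.4.3 has durations summarized by median and quartiles, and reserves between-arm differences with CIs for binary outcomes, naming new oxygen use as an example. Incidence for the whole at-risk set sits directly above the duration rows, so in step 1 a reader would see 20% and 12% first. Days of hospitalization and clinical status by visit are summarized without conditioning on new use. The note names only days on oxygen, and its reach to the other tables is by shared format. SAP Section 2.1 also announces a separate addendum on intercurrent events, which is not available here.

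Most of this stands, and it limits the weight of the point. It does not fill the gap: incidence and new-user duration can point in opposite directions, and nothing in this SAP combines them for the at-risk patients.

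A reader might infer that the rule is biased against baricitinib, or that it undermines a formal test. The documents support neither. The direction depends on which progressions are prevented, on which they give no figures. No test, power calculation or type I error allocation rests on these rows.

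**Conclusion.** The point holds as one about interpretation and completeness. In Table 42, and by inheritance in Tables 43 to 47, the duration of new support is described in groups formed after randomization. The rows can suggest longer support on an arm that reduces it, or shorter spells where none was shortened. The incidence row mitigates this in part. The size is unknown. Under the stated assumptions the new-user median moved by up to 7 days against an arm whose mean days over all at-risk patients were about 0.1 to 1.05 days lower. Those figures depend on the assumed split between mild and severe progressions and on treatment preventing only the mild ones. The primary and key secondary analyses are unaffected. The change is still worth making because these are listed secondary objectives and the remedy is cheap.

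**What to change.** In Tables 42, 44 and 46, and their subgroup versions, add a row over all randomized patients not on that support at baseline. It should give mean days on support, or support-free days to Day 29, by arm, with a between-arm difference and 95% CI. Count 0 days for never-users who survive and use the 28-day value for deaths already referred to in SAP Sections 8.2.3, 8.2.5 and 8.2.7. Do not use median and quartiles for this row. Keep the new-user rows, with a footnote that they are descriptive and not a randomized comparison.

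State how deaths without recorded support enter. New oxygen use is a score of at least 5, which as worded includes death (8), whereas the other two definitions require exactly 6 or 7.

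The cost is one row per table, a different statistic from the rest of the shell, and a little programming; no new data are needed. The downside is that the 28-day value makes the new row a composite of death and support, so show the number of deaths by arm beside it.
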